6.5 IMP risks

The Reference Safety Information (RSI) for all information pertaining to IMP risk for the XR-Bup will be set out in the manufacturer's Investigators Brochure (IB). The SmPC will be the reference document for Bup/Met.

Adverse reactions (commonly associated in 5% or more of patients) receiving XR-Bup are: (a) constipation; (b) nausea; (c) vomiting; (d) headache; (e) fatigue; (f) increased hepatic enzymes; (g) injection site pain; (h) injection site pruritis.

Drug-drug interactions potentially relevant to the IMP (with Bup and XR-Bup) are as follows:

Drug Class	Drug(s) within Class	Clinical effect and suggested management
Benzodiazepines and Other Central Nervous System (CNS) Depressants	Alcohol, non-benzodiazepine sedatives/hypnotics, anxiolytics, tranquilizers, muscle relaxants, general anaesthetics, antipsychotics, and other opioids	
 - Increases the risk of respiratory depression, profound sedation, coma, and death. - Use of these substances should be stabilised during treatment with Bup products. Patients should be advised of the danger of concomitant use of sedatives while participating in the trial.
CYP3A4 inhibitors:	Macrolide antibiotics (e.g. erythromycin) Azole-antifungal agents (e.g. ketoconazole) Protease inhibitors (e.g. ritonavir)	
 - Effects of CYP3A4 inhibitors on Bup exposure in participants treated with XR-Bup have not been studied with Bup, however, such interactions have been established. - In the presence of CYP3A4 inhibitors, monitor for signs and symptoms of Bup toxicity or overdose. - Monitor for Bup withdrawal if the concomitant medication is discontinued after the patient is stable on. - The dose of either Bup or the CYP3A4 inhibitor may need to be adjusted accordingly.
CYP3A4 Inducers	Rifampin Carbamazepine Phenytoin	
 - Effects of CYP3A4 inducers on Bup exposure in participants treated with XR-Bup have not been studied, however, CYP3A4 inducers may induce its metabolism and lead to decrease in Bup plasma concentrations. - Monitor for signs and symptoms of Bup toxicity or overdose, if the CYP3A4 inducers is discontinued after the patient is stable on XR-Bup. The dose of either Bup or the CYP3A4 inducer may need to be adjusted accordingly.

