8.2 Exclusion criteria

1. Clinically significant medical condition or observed abnormalities on physical examination or laboratory investigation, including but not limited to:
 - (a) uncontrolled hypertension, significant heart disease (including angina and myocardial infarction in past 12 months), or any cardiovascular abnormality which is judged to be clinically significant;
 - (b) severe alcohol dependence/withdrawal syndrome which is judged to be clinically significant and may constitute a risk to the patient's safety;
 - (c) acute hepatitis taken as clinical jaundice on examination, or evidence of blood bilirubin level above the normal range for local reference criteria, or evidence of serum levels of aspartate aminotransferase, alanine aminotransferase levels that are more than three-times the upper limit of the normal range;
2. History of allergic or adverse reactions to Bup or the proprietary ATRIGEL delivery system for XR-Bup (Sublocade®)*;
3. Clinically significant or uncontrolled mental health problems (including but not limited to psychosis, bipolar disorder, schizoaffective disorder), or history or evidence of organic brain disease or dementia that may compromise safety or compliance with the study protocol;
4. Current (past 30 day) suicide plan or suicide attempt in past six months;
5. Current criminal justice involvement with legal proceedings, which in the opinion of a medically qualified investigator indicates a risk that the patient would fail to complete the study protocol due to re-incarceration or move away from the centre's catchment area.
6. Currently taking oral or depot naltrexone therapy or enrolment in any form of naltrexone therapy within 90 days prior to study screening;
7. Any contraindication to Bup*.

**Participant is ineligible if they have any allergic or adverse reactions or contraindication to Buprenorphine. If participant has any allergic or adverse reaction or contraindication to Met or naloxone, or excipients of Bup-NX or Esp they can be prescribed Bup within the trial.*

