9.3 Laboratory Tests

Each site will determine all participants' liver function (as defined in the inclusion/exclusion criteria) after consent either by conducting an LFT (serum) blood-test following their local laboratory procedure, or accessing this information from the participant's hospital medical records if a prior LFT test result has been done and recorded within 12 weeks from the date of screening. During post-randomisation 6-month treatment phase, participants allocated to the XR-Bup arm will be asked to have further LFT testing at visits 4, 12 and 24, or more often as judged by the CI or PI. After the post-randomisation 6-month treatment phase, participants who consent to continue having XR-Bup injections will be asked to have further LFT testing approximately every 6 months or more often as judged by the CI or PI.

If the participant does not have their bloods taken post randomisation for any reason (i.e., including but not limited to, participant refusal, they do not attend the visit or if it is not possible to take bloods); they may continue in the trial at the discretion of the PI or Sub Investigator based on their clinical judgement. Participants randomised to BUP or Met in the study will have LFT testing according to their local standard of care.

10. Assessment of Efficacy

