11.1 Specification, timing and recording of safety parameters

For participants assigned to XR-Bup, LFT (blood sampling) will be done at screening (or recorded from the participants medical records if an LFT procedure was done no more than 12 weeks before consent), and at 4-weeks, 12-weeks and end of study (24-weeks). Participants who consent to receive XR-Bup treatment past 6 injections, a LFT will be taken every 6 months.

If a participant does not have their bloods taken for any reason post randomisation (i.e., including but not limited to, participant refusal, they do not attend the visit or if it is not possible to take bloods); they may continue in the trial at the discretion of the PI or Sub Investigator based on their clinical judgement. The CI or PI may judge that more frequent LFT monitoring is clinically indicated for these and other participants in the study.

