5.1 TIME POINTS OF OUTCOMES MEASURES

Table 2 indicates the data and study measures to be collected during the trial and at which time points across the study they are collected.

Table 1: List of outcome measures to be collected and time point of collection

Measure	Baseline	Randomisation	Ongoing	Week 1	Week 2	Week 4	Week 6	Week 8	Week 10	Week 12	Week 14	Week 16	Week 18	Week 20	Week 22	Week 24	Withdrawal	Week 24 onwards	Ext. Phase Interview ++
Consent §	X																	X	X
Screening	X																		
UDS				X	X	X	X	X	X	X	X	X	X	X	X				
LFT *	X					X				X						X		X	
BUP-XR**				X		X		X		X		X		X				X	
BUP-SL/MET **		X																	
ALC-QFM (TOP)***	X																X		
SCID-5-RV	X									X						X			X
ADAPT	X					X				X						X			
CGI-S	X																		
CGI-I						X				X						X			
CEQ-F – H***	X					X		X		X		X		X		X	X		
CEQ-F – C***	X					X		X		X		X		X		X	X		
VAS-N (H/C)***	X					X		X		X		X		X		X	X		
VAS-W (H/C)***	X					X		X		X		X		X		X	X		
DERS-SF	X					X				X						X			X
WSAS	X					X				X						X			
EQ-5D-5L	X									X						X			
AD-SUS	X									X						X			
KCF***							X			X						X			
QIDS-SR	X					X				X						X			
SURE							X			X						X			
PRO-S	X																		
PRO-I								X			X					X			
MoCA***	X									X									
OSTQOL																		X	
PHQ-4																		X	
PHQ-15																		X	
Exit Interview+																	X		
BUP-SL/MET + PSI Interview++																X			
TLFB	X	X																	X
Con Meds****		X				X				X						X		X	
Adverse Events Log		X																X	
Research Payments *****	X		X	X	X	X	X	X	X	X	X	X	X	X	X			X	
	20		10	10	10	5	10	1	10	5	10	10	10	5	10			20	

§ screening to include pregnancy test, demographics and medical history. Participants receiving XR- BUP-SL reconsented once at week 24 to continue receiving monthly injections;

* LFT for all participants at screening; during treatment for BUP-XR participants only under protocol;

** refer to section 6 of the protocol for guidelines;

*** used for mediation model;

**** ConMeds to be recorded continuously and reviewed at week 4, 12 and 24;

***** research payments are time offset to attend the clinic to complete research measures and cover travel (either a £20, £10, or £5 value, as detailed per visit applicable; loaded onto a prepaid card).

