	Day 1	day 2	Day 3	Day 4		Day 13	Day 14	Day 15	Day 16	Day 17
Self-report	drug use	drug use	drug use	drug use		no drug use	no drug use	no drug use	no drug use	drug use
UDS (Day 4 and day 16)				positive						negative

Figure 6: Example 3 of Self-report and UDS results

Outcome:	Day 1	day 2	Day 3	Day 4		Day 13	Day 14	Day 15	Day 16	Day 17
	drug use	drug use	drug use	drug use		no drug use	no drug use	no drug use	no drug use	drug use

Figure 7: Self-report and UDS example 3 outcome

The syntax for calculating this variable will be validated and verified fully prior to database lock.

During a data review it was identified that some participants had been called in for their last visit early, resulting in the full primary outcome of 161 days not being obtained. The participants in question are not lost to follow up or withdrawals and are just missing due to an administration error and in most cases only by a day or two. It was noted that patient records could provide data for some of these missing days therefore, with input from independent committees, it was decided that for the TLFB data some of the final follow up days are being input based on these medical notes.

Where the TLFB data is not obtainable from the patient notes, the missing days will be imputed using a devised rule. The missing data rule used for these missing days will look at the last 14 days of data that are available for the participant, the percentage of drug use will be calculated. For all missing days a random number will be generated (either a 0 or 1, no use or use) using a probability based on their percentage used in the last 14 days.

Measure 2; Longest time in days *continuously* abstinent from 'substance' during days 8-168 (weeks 2 to 24, 161 days); combining self-report information from time-line follow-back and 12 urine drug screen (UDS) results.

- Longest count of days continuously abstinent from illicit/non-medical opioids
- Longest count of days continuously abstinent from cocaine
- Longest count of days continuously abstinent from benzodiazepines

Secondary objectives;

Objective 1 – Clinical superiority of BUP-XR plus PSI versus BUP-SL/MET plus PSI.

Will be analysed as part of phase 2 of the study and detailed in a separate SAP

Objective 2 - Safety profile

- Tabulation of AEs, ARs, SAEs, SARs and SUSARs in each group

Objective 3 - Treatment retention

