5.3 SAFETY DATA

All adverse events, reactions and serious and unexpected events/reactions will be reported immediately following the procedure noted in the protocol (section 11.2). Safety data in the form of all AEs will be presented to the DMC on a scheduled basis. This report will cover the number of events and number of subjects affected split by treatment arm and categorised by seriousness (not serious, death, is life-threatening, requires hospitalisation or prolongation of hospitalisation, persistent or significant disability or incapacity, consists of a congenital anomaly or birth deficit, important medical event or pregnancy). Frequencies of system organ class will also be presented split by treatment arm. No statistical testing of these data will be undertaken in the DMC report. These data will also be included in the final analysis report. Precipitated withdrawal symptoms will be included in the discussion section of the primary paper as a narrative in relation to the Adverse Events table. This will not be a formal analysis but to check if there is a correlation between the first 24-48 hours prior to treatment and first

month after treatment and numbers of precipitated withdrawal symptoms reported between the treatment arms.

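### SAP 5.3 tabulates adverse events and organ classes by arm, but on-treatment liver tests are scheduled in the XR-Bup arm only, so counts that contain laboratory liver-enzyme events are not comparable between arms and carry no caveat

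*SAP*

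**What the plan says.** **Planned safety analysis.** SAP 5.2 lists under the safety objective: "Tabulation of AEs, ARs, SAEs, SARs and SUSARs in each group". SAP 5.3 plans counts of events and of participants affected, by arm and by seriousness, and adds: "Frequencies of system organ class will also be presented split by treatment arm". The same material goes to the DMC and into the final analysis report. Appendix 2 (Objective Two) classes this analysis as descriptive.

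**Liver testing.** Protocol 9.3 says that "participants allocated to the XR-Bup arm will be asked to have further LFT testing at visits 4, 12 and 24", or more often if the CI or PI so judges. For the comparator it says: "Participants randomised to BUP or Met in the study will have LFT testing according to their local standard of care". Protocol 11.1 gives its schedule for one arm: "For participants assigned to XR-Bup, LFT (blood sampling) will be done at screening", then at 4, 12 and 24 weeks. The SAP repeats the difference in the footnote to its Table 1: "LFT for all participants at screening; during treatment for BUP-XR participants only under protocol".

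**Why liver enzymes are relevant.** Protocol 6.5, listing reactions seen in 5% or more of XR-Bup patients, includes "f) increased hepatic enzymes". Protocol 8.2 excludes patients with "alanine aminotransferase levels that are more than three-times the upper limit of the normal range" (and likewise for AST), so lesser elevations are allowed at entry.

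**What is absent.** SAP 5.2, 5.3 and Appendix 2 plan no summary of LFT values and no count of participants tested. LFTs are also missing from the SAP 5.2 list of measures that are collected but analysed elsewhere. Nothing connects the Table 1 footnote to the adverse event tables.

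**The concern.** A rise in liver enzymes without symptoms is seen only if blood is taken. In XR-Bup the protocol provides three occasions for this during treatment. In the oral arm it provides none, and what local care adds is not stated. Two arms with the same underlying rate could therefore show different numbers of recorded events.

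The event concerned is one that the protocol already expects with XR-Bup, so a reader who saw an excess would naturally attribute it to the drug. Without the number tested in each arm, that reader could not separate a drug effect from a difference in testing. At stake is the reading of a descriptive safety table that serves a stated secondary objective. No hypothesis test is planned on these data in the DMC report, and the primary estimate does not use them.

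**Working it through.** The plan gives no figure to reproduce. The check is to set the two schedules side by side and then see how far the consequence depends on things the documents do not say.

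**From the documents**

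| Item | XR-Bup | Bup/Met | Source |
|---|---|---|---|
| LFT at screening | yes | yes | Protocol 9.3; SAP Table 1 footnote |
| Scheduled on-treatment LFTs | 3 | 0 | Protocol 9.3, 11.1 |
| Further LFTs | if CI or PI judges | local care | Protocol 9.3 |
| Target arm size | 152 | 152 | Protocol 5.2 |
| Event log reviewed at trial clinic visits | yes | yes | Protocol 11.2 |

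The event log is reviewed the same way in both arms. The scheduled blood test is the difference.

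**Not in the documents (assumed).** These are the chance q that a test yields a rise recorded as an adverse event, the number k of tests taken, whether rises persist, and how many XR-Bup tests are actually done. Protocol 9.3 allows participants to continue when bloods are not taken, so full uptake cannot be presumed.

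**Illustration with no drug effect and independent tests.** The proportion with at least one recorded rise is 1 − (1 − q)^k. At q = 3%, XR-Bup shows 1 − 0.97³ = 8.7%, or 0.0873 × 152 = 13.3 participants. An oral arm with one local test shows 3.0%, or 4.6 participants.

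| q | XR-Bup, k = 3 | Oral, k = 1 | Difference, k = 1 | Difference, k = 0 | Difference, k = 3 |
|---|---|---|---|---|---|
| 1% | 3.0% | 1.0% | 2.0 points | 3.0 points | 0 |
| 3% | 8.7% | 3.0% | 5.7 points | 8.7 points | 0 |
| 5% | 14.3% | 5.0% | 9.3 points | 14.3 points | 0 |

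**With 60% of XR-Bup tests taken.** The XR-Bup proportion becomes 1 − (1 − 0.6q)³, which is 1.8%, 5.3% and 8.7% for the three values of q.
- Against one local test the difference is 0.8, 2.3 and 3.7 points.
- Against three local tests it is −1.2, −3.4 and −5.5 points.

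**With persistent rises.** If the same people are raised at every test, one test finds everyone that three would find. With full uptake, both arms then show q, and the difference against one local test is nil.

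Across these inputs the artefact runs from +14.3 points through nil to −5.5 points. What is certain is that detection is unequal by design. Its size is not known, and its direction favours finding more in XR-Bup only if local care tests less than the protocol does.

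**The case against.** The strongest reply is that the schedule is openly disclosed, that testing only the depot arm is reasonable monitoring of an unlicensed product, and that the tables are descriptive. All of that stands. It limits the importance of the point, but the reader of the safety table still lacks the information needed to interpret it.

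Four further limits also stand.

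- A reader might infer that the report will show a liver-enzyme line with an excess in XR-Bup. SAP 5.3 specifies no such line. It plans counts by seriousness and by organ class, so any excess would sit inside an organ class and, diluted by other events, in the totals.
- A reader might infer that adverse reactions and participants affected carry the same excess. They need not. Under Protocol 11.2 a reaction must be related to a dose, so a rise unrelated to treatment counts only if an investigator attributes it to the drug. A participant already counted for another event adds nothing to the number affected.
- Neither document says that a raised LFT must be logged as an adverse event. If symptom-free rises are seldom logged, the artefact approaches zero.
- Rises already present at entry may well persist, which favours the case where repeat testing adds little.

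On the other side, if rises are not logged, the scheduled LFT results would appear nowhere in this SAP's planned analysis. That supports adding the summary of LFT values for its own sake.

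**Conclusion.** The point holds as a minor one. The planned by-arm safety tables compare arms in which one expected type of event is looked for unequally, and the SAP neither reports the number tested nor warns the reader. The organ class that contains liver-enzyme events is affected most, and total adverse event counts less.

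The size cannot be derived from the documents. It depends on local testing, uptake of the scheduled tests, persistence of rises and whether rises are logged, and it could be nil. The percentages above are illustrations under assumed inputs. A reader might take 8.7% against 3.0% as an expected bias; the documents do not support that, because only the 3 and 0 scheduled tests and the 152 per arm come from them. Nor do they support a claim that the trial's efficacy conclusion is at risk, since the primary analysis does not use these data.

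**What to change.** Change SAP 5.3 and Appendix 2 (Objective Two) as follows.

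1. Add an XR-Bup-only summary of AST, ALT and bilirubin at screening and weeks 4, 12 and 24, with the number tested at each visit.
2. Keep all events in the by-arm tables, but show the affected organ class and total adverse events both with and without laboratory-only liver-enzyme events. Apply the rule to both arms, whether the event was found by a scheduled or a local-care test.
3. Add a footnote: *Post-randomisation liver function tests were scheduled in the BUP-XR arm only; liver-enzyme counts should not be compared between arms.*

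Removing only events found by scheduled tests would be uneven. It would leave oral-arm events found in local care inside the comparison and could understate liver events with XR-Bup. Treating both arms alike avoids this.

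The cost is flagging laboratory-only liver events, one extra table, the with-and-without display and one footnote. No test or visit is added, and the remaining safety tables and the precipitated-withdrawal narrative stay as they are.

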6. STATISTICAL ANALYSES

6.1 ANALYSIS TIME FRAME

Table 2: Planned target timeline for analysis dependent on recruitment period

Task	*Updated following COVID recruitment pause
Last patient recruited	~October 2021
Final patient visit	~May 2022
Database Lock	~June/July 2022
Final Analysis	~August 2022

*The analysis timelines are dependent on recruitment rates, COVID-19 impacts and discussions with the funder. Delivery of the analysis report will require at least one month following database lock to complete.

6.2 BASELINE ANALYSIS

Characteristics collected at baseline will be presented descriptively both overall and by treatment arm. No statistical testing of baseline differences will be completed, only used to assess balance. Categorical variables presented using counts and percentages, continuous variables with mean, SD and range.

6.3 INTERIM ANALYSIS

There are no planned interim analyses and as such the study is not powered to achieve these. There are no planned stopping criteria based on efficacy and stopping based on safety will be guided by the DMC.

6.4 CONSORT ANALYSIS

The patient flow information, as shown in section 3.4 above as advised by CONSORT reporting standards, will be completed with values relating to participants numbers. Additionally, data will be presented on screening, eligibility, recruitment, treatment discontinuation and withdrawn/lost to follow up presented for the entire study and split by recruitment site.

Where possible reasons for ineligibility or non-recruitment will be reported. From these data related eligibility, recruitment and retention rates will be calculated and presented in the final analysis report.

6.5 DESCRIPTIVE STATISTICS

Descriptive statistics of the data will be presented in the final analysis report. This will include randomisation figures, demographics, other data characteristics of the outcome measures and data completeness levels. All will be presented overall and split by allocation group.

Figures will be presented for the Randomisation data by each stratification variable;

- Allocation group
- Centre
- Current injecting status

The following demographics and data characteristics will be presented;

- Sex at birth
- Age
- Ethnicity
- Preference of MET or BUP-SL
- Use of cocaine in the past month
- Length of treatment episode (in days)
- Age started opioid substitution therapy
- OUD medication length this episode
- Rescue medications required
- ALC-QFM (TOP) – maximum consumption

Descriptive statistics of the outcome measures will be produced for the primary and secondary variables as listed in Appendix 2.

For all statistics, continuous variables will be reported with mean values, standard deviations and ranges. Categorical variables will be presented with counts and percentages. If data are not normally distributed then medians and interquartile ranges will be reported.

Graphical representations of the objective one measures (days abstinent and longest days) will be displayed to evaluate and observe where across the study patients 'relapsed/started using again' and where withdrawals in the study were common.

In addition, we will plot a cumulative distribution function for each group on the primary outcome, other graphical representations may be used for treatment effect visualisation.

